6.2.1 Full Analysis Subset – Baseline Age \geq 5 Years

This is a subset of FAS that consists of all subjects with age \geq 5 years at baseline. PROMIS, 6MWT and FPS-R will be analyzed using this analysis set.

6.3 Safety Analysis Set

The Safety Analysis Set will consist of all randomized subjects who received at least one dose of assigned medication. Subjects will be analyzed according to the actual treatment received in the study.

6.4 Pharmacokinetic (PK) Analysis Set

The PK analysis set consists of all subjects who received at least one dose of KRN23 and had evaluable PK data.

6.5 Pharmacodynamic (PD) Analysis Set

The PD analysis set consists of all subjects who received at least one dose of study therapy and had evaluable serum data.

7 DATA SCREENING AND ACCEPTANCE

7.1 General Principles

Data will be reviewed periodically. And any questionable data will be reported to the clinical data manager promptly for query and resolution.

7.2 Handling of Missing and Incomplete Data

Missing clinical outcome data can occur for multiple reasons, including missed subject visits and scales or measures with missing item scores. Missing and incomplete data will be identified through the data quality review plan for this study. Missing and incomplete data will be identified for investigation, and possible resolution, by Data Management prior to the study database lock or snapshot.

Unless specified otherwise, only the observed data (not imputed data) will be presented in listings.

7.2.1 Missing Date Imputation for Adverse Events and Concomitant Medications

The following conventions will be used to impute missing portions of dates for adverse events and concomitant medications. Note that the imputed values outlined here may not always provide the most conservative date.

Missing Start Dates

- If the day is unknown, then:
 - If the month and year match the first dose of investigational product start date month and year in this study, then impute the day of the first dose date.
 - Otherwise, assign the first day of the month.
- If the month is unknown, then:
 - If the year matches the year of the first dose of investigational product date in this study, then impute the month and day of the first dose date in this study.
 - Otherwise, assign 'January'
- If the year is unknown, then the date will not be imputed and will be assigned a missing value.

If the imputed date is earlier than birth date, then birth date will be used. If the imputed start date is later than the end date, then the start date will be set as the same date as the end date.

Missing Stop Dates and not ongoing

- If the day is unknown, then assign the last day of the month.
- If the month is unknown, then assign 'December.'

- If the year is unknown, then the date will not be imputed and will be assigned a missing value, and the event will be considered ongoing. If the AE has been recorded as resolved/recovered, all efforts should be made to obtain the date from the Investigator.

If the resulting end date is after the date of study completion/discontinuation/data cutoff, set the imputed end date as close to the date of study completion/discontinuation/data cutoff as possible without overwriting existing information.

If the year is missing for the start date, and stop date (observed or imputed) is on or after the first dose or event is ongoing. The start date will be imputed as the first dose date.

7.2.2 Missing Causal Relationship to Investigational Product for Adverse Events

For the KRN23 group, if the causal relationship to the investigational product is missing for an AE that started on or after the date of the first dose of investigational product, a causality of “definitely related” will be assigned.

For the active control group, if the causal relationship is missing for both oral phosphate and active vitamin D for an AE that started on or after the date of the first dose of investigational product, a causality of “definitely related” will be assigned to both oral phosphate and active vitamin D. If the causal relationship is missing for one of the oral phosphate or active vitamin D medication and not missing for the other one, the missing causality will not be imputed.

The imputed values for causal relationship to investigational product will be used for the incidence summary; the values will be shown as missing in the data listings.

7.2.3 Visit Time Windows

Unscheduled visit occurred prior to or on the date of initiation of the first dose will be mapped to the baseline visit if it is the last assessment prior to or on the date of initiation of the first dose; otherwise no mapping will be performed.

Unscheduled visits that occurred after the date of initiation of the first dose will be mapped to the post-baseline scheduled visit with the closest target study day (refer to Section 5.3 for study day definition and Appendix 3 for the schedule of events). If the unscheduled visit is in the middle of two scheduled visits, map to the later scheduled visit. For PD, PK and safety assessments (refer to Section 4.2, 4.3 and 4.4), if the time difference between the unscheduled visit and closest scheduled visit is ≥ 14 days, the unscheduled visit will not be mapped.

For descriptive summary tables, when more than one measurement is mapped to the same scheduled visit, the measurement taken on the scheduled visit will be used if it is not missing, otherwise the one closest to the target day will be used. If two or more visits have equal distances to the target day, then the later one will be used. If more than one measurement is collected on the same day, use the time or the sequence number to select the latest record.

For listings and shift tables in safety analysis, all data points will be included.

Early termination visit will generally follow the same rule as unscheduled visit except for a special case in X-rays. X-rays will not be performed at the early termination visit if the assessment was conducted within 3 months of termination. Hence if a subject has X-rays at both Week 40 and early termination visits, the X-rays on early termination visit will be mapped to Week 64.

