9. For the PROMIS Pediatric Pain Interference, Fatigue, and Physical Function Mobility scales, the parent or legal guardian will complete a Parent/Legal Guardian form for subjects ages 5 to < 8 years of age at the Screening Visit. Subjects ≥ 8 years of age at the Screening Visit will complete a pediatric self-report form. Parent/Legal Guardian forms will be used for the duration of the study for subjects < 8 years of age at the Screening Visit who had a baseline assessment, even when a subject turns 8 during the study. If a subject ≥ 8 years of age at screening has difficulty completing the PROMIS self-report, the investigator may allow the PROMIS interview to be administered by trained clinic staff or allow the parent to complete the PROMIS Parent Proxy version. The reason should be carefully documented and consistent practice of administration should be maintained for every visit from Baseline.
10. If a subject is < 5 years of age at the Screening Visit and therefore has no baseline data, SF-10 will not be administered even when the subject turns 5 during the study.
11. Blood and urine to be collected after a minimum overnight fasting time of 4 hours and prior to drug administration (if applicable). Record fasting duration on CRF. Serum phosphorus may be collected as an unscheduled laboratory assessment if necessary. Details for blood and urine collection can be found in the central laboratory manual.
12. Pre- and post-prandial serum phosphorus and calcium concentrations will be assessed at a single clinic visit anytime 10 to 14 days after a KRN23 dose; this clinic visit may take the place of a Home Health visit. Approximately 20 subjects, age ≥ 3 years, will fast overnight for a minimum of 8 hours, and fasting serum will be collected prior to a breakfast containing predefined ranges of phosphate, calories, and carbohydrate representative of a typical Western diet for children. Serum samples will be drawn 1 and 2 hours after the completion of the meal (refer to Table 7.5.4.3.1).

13. Serum KRN23 concentrations and ADA assessment will be performed only for subjects randomized to KRN23 during the Treatment Period and for all subjects during the Treatment Extension Period. If development of anti-KRN23 antibodies is suspected in a given subject, samples may be obtained at additional time points on a case-by-case basis.

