7.5.4.3 Pre- and Post-prandial Serum Phosphorus and Calcium Concentrations Substudy

Pre- and post-prandial serum phosphorus and calcium concentrations will be assessed at a single clinic visit anytime 10 to 14 days after a KRN23 dose. The substudy will be conducted at sites in the US, Canada, and Australia that are able to provide and observe a nutritionally defined meal in their clinic. The substudy will be conducted in approximately 20 subjects, age ≥ 3 years.

The Investigators or Study Coordinators at the sites chosen will contact the subject/caregiver asking for participation in the substudy. If agreed, a clinic visit will be scheduled and the subject will be consented at that time and prior to any substudy assessments being conducted. The clinic visit may take the place of a Home Health visit or be at a regularly scheduled clinic visit. Before the visit at which the substudy assessments are conducted, subjects must have received at least 4 doses of KRN23 (≥ 8 weeks of treatment) with at least 80% compliance and did not miss the previous dose of KRN23.

Subjects will fast overnight for a minimum of 8 hours, and fasting serum will be collected prior to breakfast ([Table 7.5.4.3.1](#)). Meals will contain predefined ranges of phosphate, calories, and carbohydrate and will be representative of a typical Western diet for children. Subjects will have the option of 2 to 3 nutritionally defined meals (depending on the clinical site). Subjects will be given a 1-hour window to consume the meal. Dietary phosphate will be estimated based on the amount of food consumed. Serum samples will be drawn 1 and 2 hours after the completion of the meal.

Table 7.5.4.3.1: Schedule of Events for the Pre- and Post-prandial Serum Phosphorus Concentrations Substudy

	Prior to Substudy Assessments	Hour 0	Hour 1	Hour 2	Hour 3
Informed consent	X				
Serum phosphorus and calcium ¹		X			
Begin meal ²		X			
End meal ³			X		
Serum phosphorus and calcium ⁴				X	X

1. Serum collected after at least 8 hours of fasting and before meal.
2. Nutritionally defined meal typical of a Western diet for children with a known phosphate content (approximately 200 to 500 mg).
3. Meal should be completed within 1 hour. If the meal cannot be completely consumed, record the quantity consumed.
4. Serum collected 1 and 2 hours after completion of the meal.

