1 INTRODUCTION

The purpose of this Statistical Analysis Plan (SAP) is to provide details of the statistical analyses that have been outlined within the UX023-CL301 Protocol original version dated 04APR2016.

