8.5.4.7 PD Analysis

The PD parameters will include serum phosphorus, TmP/GFR, serum 1,25(OH)₂D, TRP, and ALP. All PD analyses will be performed on the PD Analysis Set, unless stated otherwise.

Descriptive statistics of PD parameters and their respective change from baseline and percentage change from baseline will be tabulated by treatment group at each study visit.

The change in serum phosphorus from baseline to mean post-baseline values (average of Week 1, 4, 8, 16, 24, 32 and 40 serum phosphorus for Week 40 analysis and Week 1, 4, 8, 16, 24, 32, 40, 52 and 64 serum phosphorus for Week 64 analysis) will be analyzed using an ANCOVA model. Treatment group, baseline age and RSS total score stratification factors will be included as independent variables, baseline serum phosphorus will be included as a continuous covariate. The estimated difference between KRN23 treatment and active control group will be provided along with 95% CI and p-value. The estimated change from baseline within individual treatment groups will also be provided.

PD endpoints at all scheduled visits will be assessed using the GEE approach as outlined in Section 8.5.1 with change from baseline value as dependent variable, baseline measures and baseline age and RSS total score stratification factors included as independent variables.

The proportion of subjects achieving the normal range (3.2-6.1 mg/dL) will be reported by treatment group at each study visit. Similarly, proportion of subjects achieving TmP/GFR within the normal range (2.6 – 4.4 mg/dL) will be reported by treatment group at each study visit.

A listing containing PD parameters such as serum phosphate level, serum 1,25(OH)₂D, TmP/GFR, TRP, and ALP will be provided for each subject.

Graphs showing the change over time in PD parameters for both observed measure and the respective change from baseline will be provided by treatment group.

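### The SAP's same-day tie-break can make a post-meal sample the visit value for serum phosphorus and calcium, and up to Week 64 only in the KRN23 arm

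*SAP*

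**What the plan says.** SAP 7.2.3 (Visit Time Windows) sets out which record stands for a visit. The paragraph is limited at its start: "For descriptive summary tables, when more than one measurement is mapped to the same scheduled visit". It then gives an order of preference. First, "the measurement taken on the scheduled visit will be used if it is not missing"; failing that, the record closest to the target day is taken. The last sentence deals with ties within a day: "If more than one measurement is collected on the same day, use the time or the sequence number to select the latest record". Fasting status plays no part in the rule.

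Protocol 7.5.4.3, added by Amendment 1 (03 November 2017), describes the meal substudy. Blood is taken after an overnight fast, a meal containing roughly 200 to 500 mg of phosphate follows, and then: "Serum samples will be drawn 1 and 2 hours after the completion of the meal". On where it may take place: "The clinic visit may take the place of a Home Health visit or be at a regularly scheduled clinic visit". Participants are about 20 children aged 3 or more, at US, Canadian and Australian sites. They must have had at least four KRN23 doses and are studied 10 to 14 days after a dose. The footnote describing these draws (number 12) is attached to the Serum Phosphorus and Serum Calcium rows of Protocol Tables 2.1 to 2.3.

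The PD endpoints carry a sampling condition in the Protocol Synopsis and again in Protocol 7.6.2.2: "Blood and urine to be collected after a minimum overnight fasting time of 4 hours", and before drug is given. SAP Appendix 3, footnote 11, repeats it. The SAP states that it details the analyses in the "UX023-CL301 Protocol original version dated 04APR2016", and it does not mention the substudy.

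**The concern.** A substudy child seen at a scheduled phosphorus visit has up to three phosphorus and three calcium results on one date. The only same-day rule in the SAP takes the last of them, drawn two hours after a meal containing phosphate. The endpoint is meant to be fasting phosphorus, and the amendment's rationale is to measure the rise after eating, so a selected post-meal value would be expected to be higher.

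The error would not be shared between the arms. Only KRN23-treated children can enter the substudy, and control children do not receive KRN23 until after Week 64. In the randomized comparison, any distortion would fall on one arm and favour it. The outputs at stake are by-visit phosphorus, the count of children in the normal range and, on the safety side, by-visit calcium. Serum phosphorus is also a key secondary endpoint ("The change in serum phosphorus from baseline to mean post-baseline values", SAP 8.5.4.7), so it matters whether the same record feeds that model.

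**Working it through.** The plan gives no figure for this point, so there is none to reproduce. The check traces the rule and then shows how far an assumed shift would be diluted.

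**1. Can the samples coincide?** Yes. Dosing is every two weeks, and clinic visits with a phosphorus draw at Weeks 8, 16, 24, 32, 40, 52 and 64 fall 14 days after the previous scheduled dose, inside the 10-14 day window. Four prior doses (Weeks 0, 2, 4 and 6) make Week 8 the earliest possible visit, so Weeks 1 and 4 cannot be affected. Week 33 is one week after the Week 32 dose and falls outside the window.

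**2. Which record does the rule pick?** It depends on labelling, which neither document specifies.

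- All three samples labelled with the scheduled visit: the preference for the scheduled-visit measurement does not separate them, and the last sentence picks the 2-hour post-meal sample.
- Post-meal samples labelled separately or as unscheduled: the scheduled fasting value takes priority and nothing goes wrong.
- Substudy held in place of a home visit with no scheduled phosphorus draw: its values cannot displace a non-missing scheduled value.

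**3. Which outputs use the rule?** The by-visit phosphorus summaries, changes and proportion within 3.2-6.1 mg/dL (SAP 8.5.4.7), and by-visit calcium (SAP 8.8.2), are descriptive and within its stated scope. For the post-baseline-mean ANCOVA and the GEE, the SAP gives no same-day rule.

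**4. How many visits could be affected?** A visit on or after 03 November 2017 requires a baseline no earlier than:

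- Week 40: 03 November 2017 minus 40 weeks = 27 January 2017
- Week 64: 03 November 2017 minus 64 weeks = 12 August 2016

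Ethics approval of the amendment (Protocol 8.1.1) would move these dates later. Enrolment dates are not given, so the number is unknown and could be zero by Week 40.

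**5. Size under assumptions.** Let r be the post-meal rise (not in the documents; assumed 0.3 to 1.0 mg/dL) and k the number of affected children among the 30 planned in the KRN23 arm (also assumed). Each child does the substudy once.

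- Shift in one visit's arm mean = (k/30) × r. With k = 10: (10/30) × 0.3 = 0.10; (10/30) × 1.0 = 0.33 mg/dL.
- Shift in the nine-visit post-baseline mean (Week 64 analysis), only if the same record also feeds that average = (k/30) × r/9. With k = 20: (20/30) × 0.3/9 = 0.02; (20/30) × 1.0/9 = 0.07 mg/dL.
- Shift in the seven-visit mean (Week 40 analysis), same condition, k = 20: (20/30) × 0.3/7 = 0.03; (20/30) × 1.0/7 = 0.10 mg/dL. This is an upper bound, since it puts every substudy child at an averaged visit by Week 40.
- Normal-range count: a fasting value of 2.9 mg/dL becomes 2.9 + 0.3 = 3.2 and is counted as normal.

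The control-arm shift is zero in each case up to Week 64.

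**The case against.** The best reply is that the plan already protects the fasting value. The latest-record sentence only breaks ties, it sits in a paragraph confined to descriptive tables, and that paragraph first prefers the scheduled-visit measurement. SAP Section 4 says data are collected according to Appendix 3, which requires fasting, pre-dose blood. The protocol lists the meal data as a separate exploratory assessment with its own schedule, and does not say that these samples enter the main laboratory dataset. A sensible programmer would leave them out.

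Much of this stands, and it rules out two stronger readings. A reader might infer that the rule turns the post-meal sample into the visit value for every child who does the substudy at a scheduled visit. The documents do not support that, because the result depends on sample labels that they do not define. A reader might also infer that the key secondary phosphorus comparison is biased. That is an ANCOVA, outside the rule's stated scope, and extending the rule to it rests only on the SAP's silence.

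What does not stand is the claim that the fasting condition settles the matter. It is an instruction for collection, and no SAP rule selects or excludes records by fasting status. At a shared visit all three samples are taken on the scheduled visit, so the scheduled-visit preference does not choose among them.

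**Conclusion.** The gap is real and conditional. Applied as written to samples that share a scheduled visit's label, the SAP's tie-break returns a non-fasting phosphorus and calcium value, against the plan's own sampling definition and, up to Week 64, in the KRN23 arm only. This is clear for the descriptive by-visit outputs. For the ANCOVA and GEE it is possible but not established.

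The size cannot be derived from the documents: the post-meal rise, the number of participants at scheduled visits and their timing are all missing. On the assumptions above, the by-visit results could move noticeably and the post-baseline mean very little. It would be tempting to set the single-visit shift of 0.10-0.33 mg/dL against the 0.7 mg/dL seen in Phase 2 and conclude that a large part of the effect is at risk. That comparison does not hold: 0.7 is a within-group change from baseline, and the shift belongs to one hypothetical visit.

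The primary RGI-C endpoint is not affected. Crossed-over control children could take part in the extension, but that lies outside this SAP's Week 40 and Week 64 analyses. Confidence is medium and priority minor to moderate.

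**What to change.** Add to SAP 7.2.3: for serum phosphorus and calcium, only the fasting, pre-dose sample (Hour 0 on a substudy day) is eligible as the visit value in by-visit tables, models and the post-baseline average. The 1-hour and 2-hour post-meal samples are excluded from visit mapping and reported only in the substudy analysis. Have the laboratory transfer flag those samples so that the exclusion can be programmed. State also that the analyses take account of Amendment 1.

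The cost is a short SAP addition and one data flag, with no change for children or sites. It removes the possible shift whatever the true post-meal rise and however the samples are labelled, and it supplies the same-day rule that the ANCOVA and GEE now lack for substudy days.

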7.3 Testing/Validation Plan

Data will be reviewed by cross functional teams periodically and issues will be addressed by clinical data management.

7.4 Software

SAS[®] software version 9.4 or higher will be used to perform statistical analyses unless otherwise specified.

8 STATISTICAL METHODS AND ANALYSES

8.1 General Principles

The efficacy analyses will be based on the full analysis set. The PD analyses will be based on the PD analysis set. The safety analyses will be based on the safety analysis set. Statistical tests will be two-sided hypothesis tests performed at the 5% level of significance for main effects. Confidence intervals will be 2-sided 95% confidence intervals, which will be provided for both within group estimate and between group difference. P-values will be rounded to and displayed in three decimals. If a p-value less than 0.0001 occurs, it will be shown in tables as <.0001. There will be no multiplicity adjustments, or adjustments for multiple comparisons. Continuous variables will be summarized by number of subjects and mean, standard deviation/standard error (SD/SE), median, Q1, Q3, minimum, and maximum values. Categorical variables will be summarized by number and percentage of subjects.

If an outlier is identified and/or a pronounced non-normal probability distribution is found for the difference between the two treatment groups, then a non-parametric analysis corresponding to that of the parametric counterpart, e.g. the Wilcoxon rank test for median, will be performed and be considered as the primary analysis to assess the treatment difference between KRN23 and active control groups. Such a model violation may be identified by graphical methods, measures of non-normality (e.g., skewness, kurtosis) or other appropriate methods.

